## 10.2. Case Report Form (CRF) Completion

A CRF is required and should be completed for each individual participant. For the LOCI trial this will be in the form of an eCRF. The data held on the completed original eCRFs are the sole property of the respective PIs whilst the data set as a whole is the property of the Sponsor and should not be made available in any form to third parties except for authorised representatives or appropriate regulatory authorities without written permission from the sponsor. Appropriate data sharing requests will be considered by the trial management group and the BCTU data sharing committee.

**LOCI PROTOCOL** Sponsor's reference: RG\_18-272 v1.0 07-Nov-2019 Page 43 of 57 IRAS ID: 257918 EudraCT number: 2018-004641-16 ISRCTN: TBC

It will be the responsibility of the investigator to ensure the accuracy of all data entered in the eCRFs and confirm accordingly. The **LOCI Site Signature & Delegation Log** will identify all those personnel with responsibilities for data collection.

Data reported on each form will be consistent with the source data and any discrepancies will be explained. All missing and ambiguous data will be queried. Staff delegated to complete eCRFs will be trained to adhere to online completion of the eCRFs in the trial database from source data. Online data entry is achieved via unique passwords and usernames which must not be shared amongst the team. All time formats, where applicable, should be in accordance with the 24 hour clock. Rounding of numbers, where applicable, should be in the normal way (i.e.  $\geq x.5$  is rounded up to the nearest whole number). Laboratory test data that is used to inform clinical decisions should always be supplied. If a test is repeated it is either to confirm or clarify a previous reading. Confirmatory tests should use the original test values. Protocol and GCP non-compliances should be added to a Protocol Deviation Log, held by the site, and reported to the Trials Office on discovery.

## 10.3. Participant completed Questionnaires

EQ-5D-5L questionnaires can be completed in clinic or by telephone. The questionnaire will be completed by the participant, and overseen by a member of the research team. At the time of completion, the member of the research team will check to make sure the questionnaire has been fully completed by the patient.

### 10.4. Data Management

Processes will be employed to facilitate the accuracy of the data included in the final report. These processes will be detailed in the trial specific Data Management Plan. Coding and validation will be agreed between the trial team and the trial database and will be signed off once the implementation of these has been assured. Data entry will be completed by site staff from source via the MedSciNet system. The data capture system will conduct automatic range checks for specific data values to ensure high levels of data quality. Queries on the trial data will be raised using the integrated data query system in the trial database, with the expectation that these queries will be completed by the site within 30 days of receipt. Overdue data queries will be requested on a monthly basis.

# 10.5. Data Security

The security of the System is governed by the policies of MedSciNet. MedSciNet's Data Protection Policy and the Conditions of Use of Computing and Network Facilities set out the security arrangements under which sensitive data should be processed and stored. All studies at the University of Birmingham have to be registered with the Data Protection Officer and data held in accordance with the General Data Protection Regulation (GDPR) 2018. The University will designate a Data Protection Officer upon registration of the study. The Study Centre has arrangements in place for the secure storage and processing of the study data which comply with the University of Birmingham policies.

**LOCI PROTOCOL** Sponsor's reference: RG\_18-272 v1.0 07-Nov-2019 Page 44 of 57 IRAS ID: 257918 EudraCT number: 2018-004641-16 ISRCTN: TBC

The System incorporates the following security countermeasures:

Physical security measures: restricted access to the building, supervised onsite repairs and storages of back-up tapes/disks are stored in a fire-proof safe.

Logical measures for access control and privilege management: including restricted accessibility, access controlled servers, separate controls used non-identifiable data etc.

Network security measures: including site firewalls, antivirus software, separate secure network protected hosting etc.

System Management: the System shall be developed by the MedSciNet and will be implemented and maintained by MedSciNet.

System Design: the system shall comprise of a database and a data entry application with firewalls, restricted access, encryption and role based security controls.

Operational Processes: the data will be processed and stored by MedSciNet, then securely transferred to the Study Centre (University of Birmingham).

Data processing: Statisticians will have access to anonymised data.

System Audit: The System shall benefit from the following internal/external audit arrangements:

- Internal audit of the system
- Periodic IT risk assessments

Data Protection Registration: The University of Birmingham has Data Protection Registration to cover the purposes of analysis and for the classes of data requested. The University's Data Protection Registration number is Z6195856.

#### 10.6. Archiving

It is the responsibility of the PI to ensure all essential trial documentation and source documents (e.g. signed ICFs, Investigator Site Files, Pharmacy Files, participants' hospital notes, copies of CRFs etc.) at their site are securely retained for at least 25 years. MedSciNet will ensure all data is securely retained for at least 25 years.

## 11. QUALITY CONTROL AND QUALITY ASSURANCE

## 11.1. Site Set-up and Initiation

All PIs will be asked to sign the necessary agreements including a Site Signature & Delegation Log between the PI and the CTU, and supply a current CV and GCP certificate to BCTU. All site staff who are performing trial specific tasks are required to sign the Site Signature and Delegation Log, which details which tasks have been delegated to them by the PI.

**LOCI PROTOCOL** Sponsor's reference: RG\_18-272 v1.0 07-Nov-2019 Page 45 of 57 IRAS ID: 257918 EudraCT number: 2018-004641-16 ISRCTN: TBC

Prior to commencing recruitment, each recruiting site will undergo a process of initiation, either a meeting or a teleconference, at which key members of the site research team are required to attend, covering aspects of the trial design, protocol procedures, adverse event reporting, collection and reporting of data and record keeping. Sites will be provided with an Investigator Site File and a Pharmacy File containing essential documentation, instructions, and other documentation required for the conduct of the trial. The BCTU trials team must be informed immediately of any change in the site research team.

## 11.2. Monitoring

The monitoring requirements for this trial have been developed following trial specific risk assessment by BCTU and as documented in the monitoring plan.

### 11.3. Onsite Monitoring

For this trial we will monitor sites in accordance with the trial risk assessment and monitoring plan. Any monitoring activities will be reported to the trials team and any issues noted will be followed up to resolution. Additional on-site monitoring visits may be triggered, for example by poor CRF return, poor data quality, low SAE reporting rates, excessive number of participant withdrawals or deviations (also defined in the monitoring plan). Investigators will allow the LOCI trial staff access to source documents as requested. The monitoring will be conducted by BCTU.

## 11.4. Central Monitoring

Trials staff will check incoming ICFs and CRFs for compliance with the protocol, data consistency, missing data and timing at a frequency and intensity determined by the Data Management Plan. Sites will be sent DCFs requesting missing data or clarification of inconsistencies or discrepancies.

## 11.5. Audit and Inspection

The Investigator will permit trial-related monitoring, audits, ethical review, and regulatory inspection(s) at their site, providing direct access to source data/documents. The investigator will comply with these visits and any required follow up. Sites are also requested to notify BCTU of any relevant inspections.

### 11.6. Notification of Serious Breaches

Sites may be suspended from further recruitment in the event of serious and persistent non-compliance with the protocol and/or GCP, and/or poor recruitment. Any major problems identified may be reported to the Trial Management Group, Trial Steering Committee, and the REC. This includes reporting serious breaches of GCP and/or the trial protocol to the REC and MHRA.

**LOCI PROTOCOL** Sponsor's reference: RG\_18-272 v1.0 07-Nov-2019 Page 46 of 57 IRAS ID: 257918 EudraCT number: 2018-004641-16 ISRCTN: TBC

In accordance with Regulation 29A of the Medicines for Human Use (Clinical Trials) Regulations 2004 and its amendments, the Sponsor of the trial is responsible for notifying the licensing authority in writing of any serious breach of the conditions and principles of GCP in connection with that trial or the protocol relating to that trial, within 7 days of becoming aware of that breach.

For the purposes of this regulation, a "serious breach" is a breach which is likely to affect;

- the safety or physical or mental integrity of the subjects of the trial;
- the scientific value of the trial

Sites are therefore requested to notify the Trials office of any suspected trial-related serious breach of GCP and/or the trial protocol. Where the Trials Office is investigating whether or not a serious breach has occurred sites are also requested to cooperate with the Trials Office in providing sufficient information to report the breach to the MHRA where required and in undertaking any corrective and/or preventive action.

## 12. END OF TRIAL DEFINITION

The end of trial is defined as the date of last data capture. This will allow sufficient time for the completion of protocol procedures, data collection and data input. The BCTU trial team will notify the main REC, MHRA and RGT within 90 days of the end of trial. Where the trial has terminated early, the Trials Office will inform the MHRA and REC within 15 days of the end of trial. The Trials Office will provide them with a summary of the clinical trial report within 12 months of the end of trial. A copy of the end of trial notification as well as the summary report will be sent to MHRA and REC.

#### 13. STATISTICAL CONSIDERATIONS

#### 13.1. Sample Size

Just under two thousand participants (n=1,992) will provide greater than 99% power (at p=0.05) to detect differences in the letrozole vs clomifene comparison (assuming rates of 39% vs 29% respectively for rate of live birth ≥34 weeks) and the same power to detect differences in the metformin vs placebo comparison (also assuming rates of 39% vs 29%, respectively). Adjusting for a worst case scenario of 5% attrition, the total number required will be 2,100 participants. The high rate of power (>99%) has been chosen to ensure we will have 90% power (p=0.05 and 1050 participants) to answer the further question of letrozole plus metformin vs clomifene plus metformin (the latter comparison assuming rates of 44% and 34%, respectively). The basis for the proportions used in these calculations is provided in the next paragraph.

**LOCI PROTOCOL** Sponsor's reference: RG\_18-272 v1.0 07-Nov-2019 Page 47 of 57 IRAS ID: 257918 EudraCT number: 2018-004641-16 ISRCTN: TBC

The live birth rates used in the sample size calculations was taken from our systematic review (Table 8). We used the estimate in the clomifene alone group (24%) as the base estimate for these calculations as this was by far the largest group involving 36 trial groups and 2299 women — it was also the most conservative estimate (lowest rate), which was important as information was only available on the rate of pregnancy and not live birth rate. A 10% absolute increase was identified in

our clinician survey as minimally important so we chose this as the difference we wanted to detect when comparing clomiphene with letrozole or with the addition of metformin (i.e. both increased to 34%). We assumed using both letrozole and metformin would have an additive effect, i.e. increased to 44%. Overall, this amounted to an assumption of 29% versus 39% in the two main comparisons (letrozole vs clomifene

**Table 8:** Meta-analysis of clinical pregnancy rates in the four arms of the proposed 2x2 factorial design trial.

Drug	Letrozole	Clomifene
Metformin	49% (95% CI 39% to 63%, 1 trial arm, 67 women)	39% (95% CI 36% to 42%, 9 trial arms, 635 women)
No metformin	35% (95% CI 33% to 38%, 8 trial arms, 832 women)	24% (95% CI 23% to 25%, 36 trial arms, 2,299 women)

and metformin vs placebo) when we take into account the factorial design (i.e. the overall rates at the margins). No interaction of the effect is assumed in these calculations as the biological mechanism of these agents is considered sufficiently different and – to our knowledge – is unlikely to have a pronounced effect on outcome.

## 13.2. Analysis of Outcome Measures

A separate Statistical Analysis Plan will be produced and will provide a more comprehensive description of the planned statistical analyses. A brief outline of these analyses is given below.

The primary comparisons will be composed of (i) those randomised to letrozole versus those randomised to clomifene; (ii) those randomised to metformin versus those randomised to placebo and (iii) randomised to letrozole plus metformin versus those randomised to clomifene plus metformin. The three comparisons are considered distinct questions and will be reported separately; hence no adjustment for multiple testing across comparisons is proposed.

In the first instance, for all three comparisons, all analyses will be based on the intention to treat principle, i.e. all participants will be analysed in the treatment group to which they were randomised irrespective of compliance or other protocol deviation. For all outcome measures, appropriate summary statistics will be presented by group (e.g. proportions/percentages, mean/standard deviation or median/interquartile range). All outcomes will be presented with point estimates (e.g. relative risks, incident rate ratios, hazard ratios, mean differences) and 95% confidence intervals. Treatment effects will be adjusted for the minimisation variables listed in section 6.2 as well as both group allocations (from the factorial randomisation) by including them in the regression models (see section 13.2.2).

For the primary outcome and the key secondary outcomes, we will incorporate a hierarchical approach to statistical testing (via analysis methods described below). That is, if the primary outcome is statistically significant (p<0.05) we will proceed to test the key secondary outcomes

**LOCI PROTOCOL** Sponsor's reference: RG\_18-272 v1.0 07-Nov-2019 Page 48 of 57 IRAS ID: 257918 EudraCT number: 2018-004641-16 ISRCTN: TBC

(pregnancy loss) without any adjustment for the overall rate of type I error (i.e. the test will be conditional and only performed if there is rejection of the primary outcome null hypothesis). Safety outcomes will be subject to statistical testing without adjustment for multiple testing as adjustment for multiplicity is counterproductive for considerations of safety. Exploratory secondary outcome will not be subject to statistical testing and will be presented for supporting evidence only (significance will not be inferred from the confidence interval width).

## 13.2.1. Primary Outcome Measure

The primary outcome is the proportion of women randomised who experience a live birth at and beyond 34 weeks of gestation. The denominator of this proportion will be all women randomised and the numerator will be those women who have conceived during the six ovulation induction cycles (maximum 240 days) and have gone on to have a live birth at or beyond 34 weeks. A log-binomial regression model will be used to calculate the adjusted relative risk and 95% confidence interval. Statistical significance of the treatment group parameter will be determined from the p-value generated by the model

## 13.2.2. Secondary and Safety Outcome Measures

For dichotomous outcome (e.g. pregnancy loss), relative risks and 95% confidence intervals will be generated in the same fashion as the primary outcome. Poisson regression will be used for count data (number of ovulation induction cycles to live birth), linear regression for continuous data (e.g. birth weight) and a Cox Proportional Hazard (PH) model (provided the assumptions of proportionality are met) for time to event data (time from randomisation to pregnancy). For the key secondary outcomes (if tested, see above) and safety outcomes the p-values from the treatment group parameters in the models will be used to determine statistical significance.

For the secondary pregnancy outcomes (such as ongoing pregnancy) the analysis population will be women who went on to achieve confirmed pregnancy. For neonatal outcomes and complication rates, twin babies – in the first instance – will both be counted in the analysis population. The effect of this will be explored through sensitivity analysis. In the event of twin babies having different pregnancy outcomes, for example one live birth and one pregnancy loss, both the events will be counted in the separate categories, i.e. they will contribute to both a live birth event and a pregnancy loss event.

# 13.2.3. Subgroup Analyses

Subgroup analyses will be restricted to the primary outcome only. BMI (<30 and ≥30) is the single key subgroup of interest (i.e. we propose to be able to draw firm conclusion about any differential effect with respect to this variable only). Other subgroup analyses will be considered exploratory. These will be limited to the same variables used in the minimisation algorithm (apart from centre; see section 6.2) and androgen excess confirmed clinically or through laboratory testing. Tests for interaction will be performed by including the treatment group by subgroup interaction parameter in the statistical model. A p-value for this parameter will be produced. Given there is only one key subgroup of interest, no adjustments will be made for multiple testing on this p-value.

**LOCI PROTOCOL** Sponsor's reference: RG\_18-272 v1.0 07-Nov-2019 Page 49 of 57 IRAS ID: 257918 EudraCT number: 2018-004641-16 ISRCTN: TBC

## 13.2.4. Missing Data and Sensitivity Analyses

Every attempt will be made to collect full follow-up data on all study participants; it is thus anticipated that missing data will be minimal. Participants with missing primary outcome data will not be included in the primary analysis in the first instance. This presents a risk of bias, and sensitivity analyses will be undertaken to assess the possible impact of the risk. In brief, this will include a multiple imputation (MI) approach. Full details will be included in the Statistical Analysis Plan.

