9.3. Handling missing data

In the first instance, analyses will be completed on received data only with every effort made to follow-up participants to minimise any potential for bias. To examine the possible impact of missing data on the results, and to make sure we are complying with the intention-to-treat principle, sensitivity analysis will be performed on the primary outcome measure.⁶ See section 9.10 for further details regarding sensitivity analyses.

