9.10. Sensitivity and supportive analyses

Sensitivity analyses will be limited to the primary outcome and will consist of:

- Per-protocol analysis; this will comprise the adherent population as described in sections 5.4;
- No interaction of treatment effect (as a result of the two trial allocations) is assumed. To explore this assumption, a treatment group interaction parameter (randomisation 1 by randomisation 2) will be added to the base model for trial comparisons A and B only as comparisons C-E only include one of the randomisations[4.13]). A p-value for this interaction parameter will be produced and examined as well as the interaction coefficient and 95% CI. If this parameter is significant, then treatment effect estimates within randomisation 2 allocation (for randomisation 1) and randomisation 1 allocation (for randomisation 2) will be explored as per the subgroup analysis methods described in section 9.9. It should be acknowledged that any test for interaction will be underpowered to detect a significant effect.
- An analysis to assess the effect of missing responses for the primary outcome only. Unadjusted models will be utilised. This analysis will explore the possibility that missing

responses are 'missing not at random' (MNAR) using a tipping point approach. In this analysis, for women with missing outcome data, events will be added sequentially in each of the groups in turn to determine the point where the general conclusion changes (for example from positive to inconclusive in terms of the CI). An assessment can then be made about whether the event rate in the missing responses between groups is likely to be plausible when compared with the event rate in the non-missing data. Two scenarios will be considered as follows:

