- Scenario A: In the 'treatment A' group, assume all missing responses are nonevents (i.e. women randomised who experience a live birth is no). For missing responses in the 'treatment B' group, we will first replace X missing responses with events (i.e. X additional cases of live birth) where X is the number of events such that the event rate in the missing responses is equal to the event rate in the non-missing responses in the 'treatment B' group. This will be regarded as the base case. All other missing responses in the 'treatment B' group will be considered as non-events. An unadjusted model will be fitted. Event rates will be compared between groups. The CI from the treatment estimate (from the RR of the log-binomial model) will be examined and stored. Following the base case, an additional event will be added to the 'treatment B' group and the above procedure repeated (unadjusted model fitted and the RR and CI examined). This process will end when the number of events added to the 'treatment B' group are equal to the original number of missing responses in this group. The tipping point for the 'treatment B' group will occur when enough events have been added such that the upper/lower limit of the CI from the corresponding model differs from that of the primary ITT finding (in regards to whether the CI crosses the null value of one).

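### The SAP omits, without explanation, the multiple-imputation analysis promised in protocol v1.0, and its tipping-point analysis takes no account of known pregnancy status

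*Protocol*

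**What the plan says.** Protocol section 13.2.4 sets a complete-case primary analysis: "Participants with missing primary outcome data will not be included in the primary analysis in the first instance". It names this as a risk of bias and answers it with a commitment: "In brief, this will include a multiple imputation (MI) approach. Full details will be included in the Statistical Analysis Plan".

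SAP section 9.3 keeps the complete-case start ("In the first instance, analyses will be completed on received data only") and refers to section 9.10 for sensitivity analyses. Section 9.10 lists a per-protocol analysis, a test of interaction between the two randomisations, and one missing-data analysis: "An analysis to assess the effect of missing responses for the primary outcome only. Unadjusted models will be utilised". This last is a tipping-point analysis for outcomes missing not at random (MNAR), with two mirror-image scenarios. In Scenario A, "In the 'treatment A' group, assume all missing responses are nonevents". The other arm starts from a base case in which "the event rate in the missing responses is equal to the event rate in the non-missing responses" for that arm, and events are then added one at a time. At each step, "The CI from the treatment estimate (from the RR of the log-binomial model) will be examined and stored". Whether a tipping point is plausible is judged by comparing the event rate assumed for the missing women with the rate in the non-missing data.

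Multiple imputation appears nowhere in the SAP. In the protocol, its only other appearance is in the economic evaluation (section 13.5).

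SAP section 9.4 shows that pregnancy status is recorded separately from birth outcome: the positive test and its date on Form 04, the 11-14 week scan with fetal heartbeat on Form 05, and the birth on Form 07.

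**The concern.** The protocol identifies a bias and names the remedy; the SAP carries out a different analysis and does not say why. The two are not interchangeable. Multiple imputation under MAR would give an adjusted estimate that uses what is known about each woman before she was lost. In the tipping point, one arm's missing women are all non-events, so neither scenario is a MAR estimate, and no covariate enters.

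Pregnancy status matters because it is the strongest information available on a missing live birth. A woman lost after a positive test is far more likely to have had the event than the average randomised woman. A single overall rate, used both as the base case and as the yardstick for plausibility, describes her badly. The more effective arm also has more pregnancies in which follow-up can be lost. At stake are the arm-level live-birth rates, the risk difference if losses differ by arm, and the reading of a tipping point in comparison C (letrozole plus metformin against clomifene plus metformin), which has the least power.

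**Working it through.** **The plan's own figures (SAP 4.7).** Power = Φ[(d√n − 1.96√(2p̄(1−p̄))) / √(p₁q₁ + p₂q₂)], two-sided 5%.
- 39% vs 29%, n = 760 per arm: (2.757 − 1.313)/0.666 = 2.17, power 98.5% (stated 98.5%).
- 44% vs 34%, n = 380 per arm: (1.949 − 1.352)/0.686 = 0.87, power 80.8% (stated 81%).
- 1,520/0.95 = 1,600 and 760/0.95 = 800.

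These reproduce. At 5% loss, about 40 women per arm lack the outcome in each main comparison and about 20 per arm in comparison C.

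**Live births per conception (protocol 1.2.2, cited three-arm trial).** Clomifene 47/62 = 76%; metformin plus clomifene 56/80 = 70%; pooled 103/142 = 73%.

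**Effect on the complete-case rates.** Let p be the true rate, c = p/0.73 the conception rate, l the loss among conceivers and o the loss among the others. Loss is taken as random within each group.
- Missing fraction m = c·l + (1 − c)·o
- Complete-case rate = p(1 − l)/(1 − m)

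With true rates 39% and 29%, c = 0.534 and 0.397. The loss rates are assumptions; the documents give none by arm or by pregnancy status.

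| Conceivers lost, letrozole vs clomifene | Others lost | Missing overall | Complete-case rates | RD (points) | RR |
|---|---|---|---|---|---|
| none | none | 0% | 39.0 vs 29.0 | 10.0 | 1.34 |
| (a) 10% vs 10% | 0% | 4.7% | 37.1 vs 27.2 | 9.9 | 1.36 |
| (b) 12% vs 6% | 2% | 5.5% | 37.0 vs 28.3 | 8.8 | 1.31 |
| (c) 15% vs 5% | 0% | 5.0% | 36.0 vs 28.1 | 7.9 | 1.28 |

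Example, (a): 0.39 × 0.90/(1 − 0.0534) = 0.371 and 0.29 × 0.90/(1 − 0.0397) = 0.272, which are 1.9 and 1.8 points too low. Using 70% or 76% in place of 73% moves the RD by about 0.1 point or less.

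The direction is not fixed. Reversing (c) to 5% vs 15% gives 0.39 × 0.95/(1 − 0.0267) = 0.381 and 0.29 × 0.85/(1 − 0.0596) = 0.262, an RD of 11.9 points (0.1185 before rounding).

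**What the tipping point would show.** Unadjusted RR with a log-scale Wald interval, SE = √(1/a − 1/n + 1/b − 1/m) for a/n and b/m events. SAP treatment A is taken as the letrozole arm.

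*Comparison A*, 760 observed and 40 missing per arm (296.4 and 220.4 events): complete case 1.345 (1.166 to 1.551).
- Scenario A runs from 1.278 (1.109 to 1.471) to 1.138 (0.995 to 1.302).
- Scenario B runs from 1.416 (1.228 to 1.631) to 1.526 (1.329 to 1.753).
- Filling the missing women at 70% to 76%, as if all were lost after conceiving, gives 1.30 to 1.31. If that holds in the letrozole arm only, with the other arm's missing women non-events, it gives 1.47 to 1.48; in the clomifene arm only, 1.18 to 1.19. All lie within the range of the two scenarios.

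*Comparison C*, 380 observed and 20 missing per arm (167.2 and 129.2 events): complete case 1.294 (1.081 to 1.550). In Scenario A, with k events added to the clomifene-plus-metformin arm:
- k = 6.8 (base case, 34% of 20): 1.229 (1.028 to 1.470)
- k = 10: lower limit 1.006
- k = 11: lower limit just under 1 (0.9996), so the result tips
- k = 14 (70%): 1.17 (0.98 to 1.39); k = 15.2 (76%): 1.16 (0.97 to 1.38)

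The tip falls at 11/20 = 55%. Against the 34% overall yardstick that looks implausible. Against 70% to 76% it does not, if about three quarters of those 20 women were lost after conceiving: 11/(20 × 0.73) = 0.75. The reading therefore turns on pregnancy status, which the plan does not bring in.

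**The case against.** The strongest reply is that the tipping point already covers the problem, and more widely than imputation would. It puts every missing woman back, refits the model at each step and runs to the extremes; every pregnancy-informed fill above falls inside its range. That stands. A reader might infer that the complete-case estimate is never recomputed, but section 9.10 does recompute the RR and its interval. What is absent is a MAR estimate and a yardstick that fits the women concerned.

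A reader might also infer that the pregnancy data are collected and left unused. They are not: Form 04 feeds time and cycles to pregnancy, Form 05 feeds ongoing and multiple pregnancy, and SAP 5.3 plans live birth among women with a positive test as supportive evidence. They are only not used to inform a missing live birth. Nor is a woman known not to have conceived within the window missing; under the numerator in SAP 9.5 she is a known non-event. The missing women are those lost after conceiving and those whose conception status is unresolved.

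The protocol supplied is v1.0 of November 2019. The SAP postdates the February 2023 sample-size change and is to be read with the current protocol, so the commitment may since have been altered. The documents cannot show this. If it was, a sentence of justification settles the departure but not the yardstick.

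The loss patterns are invented, in a double-blind trial, and (b) exceeds the plan's 5% worst case. The 73% is any live birth per conception in one trial, not births at 34 weeks or later, and that trial's metformin-alone arm gives 15/25 = 60%. These points limit the size, not the gap.

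Finally, MAR may fail if women who miscarry are likelier to lose contact. That is a reason to keep the tipping point beside the imputation.

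**Conclusion.** The point holds as an unexplained departure from protocol v1.0 that is cheap to repair. The SAP leaves out a remedy for a bias the protocol itself names, and its substitute neither gives a MAR estimate nor distinguishes women lost after conception.

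The likely effect on the treatment contrast is small. With equal loss of conceivers (10%), arm rates are 1.8 to 1.9 points too low and the RD moves 0.1 point. Only unequal loss moves it materially: to 8.8 or 7.9 points in the two illustrations, and upwards if the imbalance is reversed. These figures assume 39% vs 29%, 73% live births per conception and loss at random within conceivers and within the others.

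A reader might infer that the trial's estimates are biased in a known direction or that its main conclusions are at risk. The documents do not support that: they give no loss by arm or pregnancy status. In comparison A, Scenario A tips only near its extreme end. Comparison C is more sensitive, but its reversal above needs all missing women in the letrozole-plus-metformin arm to be non-events and most of those in the other arm to have been lost after conceiving.

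**What to change.** Keep the tipping point. Add to SAP 9.10, before unblinding, a multiple-imputation analysis of the primary outcome under MAR for comparisons A to C:
- **Imputation model:** the allocation (for A and B, both allocations and their product), the minimisation factors, completed cycles, positive pregnancy test and viable 11-14 week scan.
- **Reporting:** pooled adjusted RR and RD with 95% confidence intervals, beside the complete-case result.
- **Tipping-point plausibility:** judged separately for women lost after conception and women lost with conception status unresolved, for example using the live-birth rate per pregnancy already planned in SAP 5.3 for the first group.

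If imputation was dropped on purpose, record the reason and the protocol version that changed it; the separate plausibility judgement is still needed.

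The cost is SAP wording and modest programming on data already collected. Because the imputation rests on MAR, it supplements the tipping point and does not replace it.
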